# 4.5 Clinical Management of Pregnancy

All female participants of childbearing age who are sexually active will be asked to use contraception during the duration of the study and for 1 month afterwards as the effects of Coenzyme Q10 and Nicotinamide Riboside on fetal development are not clear.

Any females who become pregnant during the study period will stop taking the study product, but will continue with study procedures with the exception of the MRS procedures.

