# 3.2 Exclusion Criteria

- Pregnant
- On chronic dialysis
- Expectation to start dialysis within 6 months
- Insulin dependent diabetes
- Severe anemia: hemoglobin <8gm/dL
- Hyperkalemia: K>5.7
- Kidney transplantation
- Weight >300 lbs
- HIV
- End stage liver disease with cirrhosis
- Oxygen-dependent COPD
- Unable to walk unassisted from room to room in own house
- Institutionalization, or inability to consent
- Use of immunosuppressive medications (i.e. steroids, calcineurin inhibitors)
- Malignancy requiring active treatment or currently under surveillance at the discretion of the investigator
- Pacemaker
- Current participation in another interventional trial
- Non-English speaking
- Hospitalization for heart attack, stroke, or unstable cardiac chest pain in last 3 months (e.g. myocardial infarction, unstable angina, cerebrovascular accident)
- Any severe medical condition that the investigator feels would disqualify a patient from aggressive exercise.
- Baseline systolic blood pressure >170 or diastolic blood pressure >100
- Persistent or permanent uncontrolled arrhythmia at the discretion of the investigator.

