# 3.6 Participant Withdrawal

Participants will be allowed to voluntarily withdraw from the study for any reason and at any time. The investigator may withdraw participants from the study in order to protect their safety or if they are unwilling or unable to comply with required study procedures after consultation with the study sponsors and co-sponsors. Participants also may be withdrawn if the study sponsor, government or regulatory authorities, or site IRBs/ECs terminate the study before the planned end date. Reasons for withdrawal from the study will be recorded and a final evaluation will be made if feasible.

Participants who discontinue treatment but remain in the study will continue to be followed-up whenever possible.

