# 4.3 Adherence Assessment

Adherence to the study treatment will be assessed by study coordinator phone call midway through each treatment arm to assess adherence and inventory method to assess remaining medication/placebo at the end of the study. Adherence will be defined as consumption of at least 75% of the prescribed regimen. Up to 36 participants may be recruited to compensate for non-adherence or drop-out with the goal of 10 individuals completing in each treatment arm. Participants will be asked to bring in unused study drugs at each visit to return to IDS.

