### Screening visit procedures:

- Verification of inclusion and exclusion criteria as outline in sections 3.1 & 3.2 including
- Vital signs and anthropometrics
- 6-minute walk: Participants able to walk 500 meters or more during 6 minutes will be excluded from the study
- *Screening labs (if 6 minute walk <500meters or less):* A renal panel & Complete blood count (CBC)
- Bicycle ergometry practice: The exercise trainer will help familiarize the participant with the bicycle to mitigate significant training effects due to lack of exposure to the equipment
- Questionnaires will be handed out to be returned at the baseline visit. Participants may also choose to complete these at the baseline or online via RedCap ITHS
  - Medical History Questionnaire
  - o Kansas City Cardiomyopathy Questionnaire

Eligibility for the study will be at the discretion of the principal investigator or study clinician after review of the pertinent labs and inclusion/exclusion criteria.

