### Baseline visit

The baseline visit will be the same as visits 2-4 with an additional of medical history and anthropomorphic testing. Subject will undergo a baseline evaluation including a detailed assessment of demographics, smoking history, medical history, medication inventory, vital signs and anthropometrics (height, weight, waist to hip ratio). A pregnancy test will be performed on all women of childbearing potential. If the subjects meet the eligibility criteria the study coordinator will contact the subjects' primary physician regarding the subjects' involvement in the trial.

The study drug dispensed at Baseline visit and Visits 2, 3, 4. The participant will receive either placebo or NR or Coenzyme Q10 from the Investigational Drug Service (IDS) and instructed on how to appropriately administer the medications. He or she will be instructed to take the medication daily starting on the day after the study visit.

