# Baseline visit and Post-treatment visits (2, 3, 4)

The participant will have been required to fast for at least 6 hrs prior to each visit and abstain from caffeine or smoking before bicycle ergometry testing. Patient should avoid exercise 48hours prior to cycle ergometry. Treatment will be dispensed after cycle

ergometry at baseline and post-treatment visits 2,3 and 4. The following data will be obtained:

- Vital signs.
- Fasting blood collection for banked plasma and peripheral blood mitochondrial energetics.
- Anthropometrics (height and weight and waist to hip ratio)
- Urine pregnancy test will be given to women of child-bearing potential
- Resting energy expenditure (REE) and cycle ergometry will be performed at the Prevention center.
- The optional MRS and Muscle Fatigue tests will occur at the diagnostic imaging center at UWMC at baseline and in the same week of visits 2, 3 and 4 while patient remains on study drug. Patient should wait avoid heavy exercise for 48hrs before MRS.
- Questionnaires will be administered (PROMIS fatigue short form 17, PROMIS physical function short form 20a, and Kansas city heart failure questionnaire)

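### Section 4.5 drops only MRS for a participant who becomes pregnant, so by default she still rides the cycle test to exhaustion

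*Combined protocol and SAP*

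**What the plan says.** Section 4.5 asks sexually active women of childbearing age to use contraception. It then sets the rule for a pregnancy during the study: she stops product but "will continue with study procedures with the exception of the MRS procedures". MRS is the only procedure named as an exception.

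The procedures she would continue are those in section 5.0. For baseline and visits 2, 3 and 4 the list includes this item: "Resting energy expenditure (REE) and cycle ergometry will be performed at the Prevention center". Table 1 marks the bicycle VO2max test at the same four visits. Sections 5.0 and 7.2.2 both describe an incremental ride to volitional exhaustion, and the minimum goal for a valid VO2max is a perceived exertion of 17 (6 to 20 scale) or a respiratory exchange ratio of at least 1.

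Pregnancy testing is scheduled. Under the baseline visit the protocol says: "A pregnancy test will be performed on all women of childbearing potential". A urine test is also listed for visits 2 to 4. The screening laboratory work is limited to "A renal panel & Complete blood count (CBC").

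Section 3.2 excludes pregnant women at entry. Separately, it excludes any severe medical condition that in the investigator's view "would disqualify a patient from aggressive exercise". Section 3.6 lets the investigator withdraw a participant "in order to protect their safety" and lets her withdraw at any time.

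**The concern.** The authors considered which procedures to drop in pregnancy and named one. The wording is affirmative, so site staff who follow it would put a pregnant participant on the bicycle for a maximal test at each remaining visit. No section says that the pregnancy test is read before the ride, or that a positive result cancels it.

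What is at stake is participant safety in a rare situation; the trial's conclusions are not affected. The rides that the rule preserves also tell the trial little about the assigned treatment, because product stops once pregnancy is known.

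**Working it through.** **The rule.** No calculation is needed to establish the point; the sections are read against each other.

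- Section 4.5: all procedures continue except MRS.
- Section 5.0 and Table 1: cycle ergometry is a procedure at baseline and visits 2, 3 and 4.
- Sections 5.0 and 7.2.2: the ride goes to volitional exhaustion. The step size differs (30 W in one, 25 W in the other), which does not matter here.
- Sections 3.2, 3.6, 4.4, 6.1 and 6.2: none exempts a pregnant participant from the ride. The 3.2 criteria apply at entry. The 3.6 power is discretionary and removes her from the whole study, not from one test.

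The default is therefore that she rides.

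**Rides affected per participant.** Suppose the first positive test is at a study visit and product stops that day.

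| First positive test | Rides left, including that day | Of these, off product |
|---|---|---|
| Visit 2 | 3 | 2 |
| Visit 3 | 2 | 1 |
| Visit 4 | 1 | 0 |

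At most one remaining ride is on the assigned product. If she reports the pregnancy between visits, none is.

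**What withholding the rides would cost.** Planned post-treatment rides: 30 participants × 3 visits = 90. The loss per affected participant is 1/90 = 1.1%, 2/90 = 2.2% or 3/90 = 3.3%. The documents give no expected number of pregnancies. For an assumed 0, 1, 2 or 3 affected participants, at most 0, 3, 6 or 9 of 90 values are lost (0%, 3.3%, 6.7%, 10.0%).

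**Effect on power.** Inputs from section 7.3: SD of the within-person difference 2.1 ml/kg/min, two-sided 0.05, planned difference 2.1 ml/kg/min (1 SD). Method: paired t test with n − 1 degrees of freedom and noncentrality (difference / SD) × √n.

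This first reproduces the 80% column of Table 3:

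- n = 10 at 1 SD: power 0.803
- n = 16 at 0.75 SD: power 0.801
- n = 34 at 0.5 SD: power 0.808

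Then take the worst case, in which each affected participant drops out of a treatment contrast entirely:

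| Evaluable n | Detectable at 80% power (SD units) | Detectable (ml/kg/min) | Power at 2.1 ml/kg/min |
|---|---|---|---|
| 30 | 0.529 | 1.11 | 0.9996 |
| 29 | 0.539 | 1.13 | 0.9994 |
| 28 | 0.549 | 1.15 | 0.9991 |
| 27 | 0.560 | 1.18 | 0.9988 |

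For example, at n = 27: 0.560 × 2.1 = 1.18. These figures price the remedy. They say nothing about the size of any harm.

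**The case against.** The strongest reply is that the documents nowhere say that exhaustive cycling is unsafe in pregnancy. The only pregnancy rationale they give is uncertainty about drug effects on the fetus, and 4.5 deals with that by stopping product. The exercise-related exclusion in 3.2 is about severe medical conditions and does not mention pregnancy. The investigator can withdraw her, she can leave, and she decides when the ride ends. For an event that may never occur, discretion is a legitimate way to manage it.

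Much of this stands. The documented harm is nil, so the case for change rests on prudence: the protocol excludes pregnancy at entry and drops MRS in pregnancy, even though section 8.2 says the MR study uses no intravenous contrast. Keeping a maximal exercise test as the default fits poorly with that caution. Discretion softens the rule but leaves it in place.

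Two side points also have some force.

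- **Loss of the primary measurement.** Section 3.6 says: "Participants who discontinue treatment but remain in the study will continue to be followed-up whenever possible". Withholding the ride loses VO2max, the main outcome, from that visit on. Calling off-product rides of little use presumes interest in on-treatment values, and no section restricts the analysis to these. Under a treatment-policy reading, the lost values are a real cost, though a small one.
- **Baseline.** A woman who tests positive at baseline is already ineligible, screening includes verification of the entry criteria, and the urine test is listed above the ride. But the list is not stated to be in time order, and the first pregnancy test the documents name is at the visit with the first full cycle test. Stating the order there only enforces the existing exclusion.

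**Conclusion.** The concern holds as a matter of wording. Section 4.5 makes a maximal cycle test the default for a participant who becomes pregnant, and nothing elsewhere exempts her. It is an optional improvement. The number affected is not given and may be zero, no harm is quantified, and no trial conclusion turns on it. Confidence in the textual reading is high. The need to amend is a judgement of prudence, supported mainly by how little the change costs. The cost figures assume 0 to 3 affected participants, the plan's SD of 2.1 ml/kg/min, and complete loss of each affected participant from a contrast.

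**What to change.** 1. In section 4.5, extend the exception to *the MRS and cycle ergometry procedures*. Keep blood, urine, questionnaires and safety follow-up, in line with 3.6.
2. In section 5.0, add one sentence: for women of childbearing potential, the urine pregnancy test already scheduled at baseline and visits 2 to 4 is read before the ride, and the ride is withheld if it is positive.

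The cost is a short amendment, with no new test or visit. Each affected participant loses 1 to 3 post-treatment VO2max values, at most one of them on product. Section 4.3 already provides a margin: "Up to 36 participants may be recruited to compensate for non-adherence or drop-out". Even with 27 evaluable participants, power at the planned difference stays above 0.998.

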### 4.6 Concomitant Medications

Enrolled study participants may continue use of all concomitant medications — except those listed under criteria for exclusion or treatment discontinuation — during this study.

All concomitant medications taken or received by participants within the 4 weeks prior to study enrollment will be reported on applicable study case report forms. In addition to prescribed and over-the-counter medications (vitamins, herbal remedies, and other traditional preparations) will be recorded. Alcohol and recreational or street drug use will be recorded in clinical progress notes if needed for interpretation/documentation of observed participant health status. Medications used for the treatment of AEs that occur during study participation also will be recorded on applicable study case report forms.

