# 2.0 STUDY OBJECTIVES AND DESIGN

# 2.1 Primary Objectives

The primary objectives of this study are to:.

- To test if NR or CoQ10 supplementation improves aerobic capacity by cycle ergometry testing compared with placebo.
- To test if NR or CoQ10 improves muscle work efficiency by bicycle ergometry

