# **Optional Procedures:**

A subset of participants (N=20) may choose to undergo the following muscle imaging procedures. Subjects will go to the UW DISC lab for testing +/-3 days from each scheduled visit (Baseline – visit 4).

*Magnetic Resonance Spectroscopy:* Leg MRS will serve as a secondary outcome and optional. All participants will be offered the option to receiving leg MRS. As mentioned above, only 4 MRS will be obtained as part of this study (at Baseline, visit 2, 4 and 6). MRS will be used to measure phosphorylation capacity (ATPmax) tibialis anterior leg skeletal muscle. These functional tests assist to perturb the cell physiological state in order to measure the contents and dynamics of key metabolic compounds important in mitochondrial energy flux. P MRS is reliable with a documented coefficient of variation for oxidative phosphorylation of 5.1% and has a strong correlation with V02max. Scheduling of this test should be coordinated with [name] ([contact]).

*Muscle Fatigue:* We will test muscle fatigability at each follow-up visit. We will test the TA (tibialis anterior) leg muscle and determine the isometric force generated at 70% of maximal voluntary contraction (MVC) against a force transducer. Using labview software to measure and record the force-time waveform of each contraction we will initiate the protocol at 50 contractions per minute at 70% MVC for one minute. At each 1 minute increment will increase the contraction rate by 10 contractions per minute and reassess the subjects relative perceived exertion on a scale of 1-10 until the patient can no longer maintain the contraction waveform.

				Treatment arm 1 (6wk +/-7d)	Treatment arm 2 (6wk +/-7d)	Treatment arm 3 (6wk +/-7d)
	Screen Day -28	Baseline	Optional MRS visit	Day 1 Visit 2 Week 6 (+/-7d)	Wk 8 Visit 3 Week 13 (+/-7d)	Wk 15 Visit 4 Week 20 (+/-7d)
Time	1-1.5hr	3hr	1-2hr	3hr	3hr	3hr
Location	PC	PC	UWMC	PC	PC	PC
Compensation	\$10	\$50	\$50	\$100	\$100	\$100
Consent	Х					
Practice bicycle	Х					
Screeninglabs	Х					
Medical history		Х				
Medicine inventory		Х				
Vital signs/Anthro	Х	Х		Х	Х	Х
Product dispensed		Х		Х	Х	
Assess AEs				Х	Х	Х
Bicycle Vo2max/work		Х		Х	Х	X
REE		Х		Х	Х	Х
PBMC bioenergetics**		Х		Х	Х	Х
31P MRS (subgroup)*			Х	X (UWMC)	X (UWMC)	X (UWMC
mRNA (paxgene)		Х		Х	Х	X
Blood		Х		Х	Х	X
Urine		Х		Х	Х	X
Drug level/NAD		Х		Х	Х	X
PROMIS Fatigue/PF PRO	landout	Х		Х	Х	Х

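### The concomitant-medication rule lets a user of non-study CoQ10 or NR enrol and keep taking it in every period, including placebo; this can dilute that agent's contrast, by an amount the documents do not allow one to estimate

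*Combined protocol and SAP*

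**What the plan says.** The primary objective in section 2.1 is a comparison with placebo: "To test if NR or CoQ10 supplementation improves aerobic capacity by cycle ergometry testing compared with placebo".

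Section 4.6 sets the rule for other products: "Enrolled study participants may continue use of all concomitant medications", "except those listed under criteria for exclusion or treatment discontinuation". Section 3.2 contains one medication class, "Use of immunosuppressive medications (i.e. steroids, calcineurin inhibitors"). It does not mention CoQ10 or NR. I found no list of products that would lead to treatment discontinuation.

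Supplements are covered by recording only. Section 4.6 says of "over-the-counter medications (vitamins, herbal remedies, and other traditional preparations) will be recorded", with no restriction. The recording window it states is "All concomitant medications taken or received by participants within the 4 weeks prior to study enrollment". Medications used to treat adverse events during the study are also recorded.

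In Table 1 the "Medicine inventory" row is marked at baseline only, which agrees with the visit descriptions in section 5.0. The "Drug level/NAD" row is marked at baseline and at visits 2, 3 and 4.

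Sections 3.2 and 3.4 bar participation in other trials. They do not deal with products that participants buy for themselves.

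**The concern.** Both study agents can be taken as supplements: the NR used here is a branded product, and the reference list describes NR as a nutritional supplement. Under the rule as written, someone already taking one of them can enrol and stay on it in all three periods and in both washouts.

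For that participant the comparison becomes study dose plus own supply against own supply alone. That is a different question from the one in section 2.1. If a person who is already supplemented responds less to the added dose, the average contrast for that agent moves toward zero. The NAD and drug-level comparisons are also affected, because the values they are compared with (baseline and placebo) may already be raised.

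A participant who starts or stops a supplement between periods would add noise or bias to the within-person differences. With no inventory scheduled after baseline, this could go unseen.

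**Working it through.** **1. Can a user enrol and continue?** Section 4.6 permits everything outside the exclusion and discontinuation criteria. Section 3.2 does not list CoQ10 or NR, and no discontinuation list exists. So yes, in every period.

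**2. Reproducing the plan's sample-size figures.** Inputs from section 7.3: SD of the within-person difference 2.1 ml/kg/min, two-sided alpha 0.05, n = 30. With a paired t-test, power = 1 − F(t_crit; n − 1, d√n). Here F is the noncentral t distribution function, d is the difference in SD units, and t_crit = 2.045 at n = 30. The smallest n reaching each power is:

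| d | 80% | 90% |
|---|---|---|
| 0.5 | 34 | 44 |
| 0.75 | 16 | 21 |
| 1 | 10 | 13 |

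All six cells of Table 3 are matched. At n = 30, power for d = 1 is 99.96%. The difference that 30 participants detect with 80% power is d = 0.529, or 0.529 × 2.1 = 1.11 ml/kg/min.

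**3. Dilution, worst case.** Assumption: a share f of participants uses one agent throughout and gains nothing from the study supply of it. The documents give no value for f; 5, 10 and 20% are illustrations. The mean contrast becomes d(1 − f). Mixing responders and non-responders raises the SD by the factor √(1 + f(1 − f)d²), so power is shown without and with that inflation.

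| f | Contrast if true effect is 2.1 | Power at 1 SD | Same, mixture SD | Power at 0.53 SD | Same, mixture SD |
|---|---|---|---|---|---|
| 0 | 2.10 | 99.96% | 99.96% | 80% | 80% |
| 5% | 2.1 × 0.95 = 1.995 | 99.9% | 99.8% | 76% | 75% |
| 10% | 2.1 × 0.90 = 1.89 | 99.7% | 99.5% | 71% | 70% |
| 20% | 2.1 × 0.80 = 1.68 | 98.8% | 97.6% | 61% | 59% |

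Example for the last cell: d = 0.529 × 0.80 = 0.423; SD factor √(1 + 0.16 × 0.529²) = 1.022; 0.423 / 1.022 = 0.414; power 59%.

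At 0.53 SD with the mixture SD, the n needed for 80% power rises from 30 to 34, 38 and 48.

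**4. Partial loss.** If users lose half the benefit, the factor is 1 − f/2. Power at 0.53 SD is then 78, 76 and 71% for f = 5, 10 and 20% (SD unchanged).

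**5. Which contrast.** Own CoQ10 bears mainly on CoQ10 against placebo, and own NR on NR against placebo. The share f is therefore specific to one agent.

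**The case against.** The strongest reply is that a crossover protects against this. Each participant is their own control. Stable intake is present in every period, and if effects are additive it cancels, leaving the full effect of the study dose. This stands as a limit: dilution needs a ceiling or a reduced response in users. Section 1.3 bases supplementation on deficiency of these substances, which makes a reduced response plausible but does not prove it.

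Second, the plan has safeguards. Over-the-counter products are recorded, medications are inventoried at baseline, and drug level/NAD is sampled at four visits, so baseline use can be identified. That is fair, but no eligibility or analysis rule acts on any of these data, and no inventory is scheduled after baseline.

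Third, at the planned effect the power loss is negligible. This also stands. The planned effect of 1 SD is large, however. Table 3 takes its SD from a study of a 12-month exercise programme, not of a supplement, so smaller effects deserve a look.

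Three stronger readings are tempting, and the documents do not support them:

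- A reader might infer that the rule dilutes both contrasts. One user of one product need not affect the other agent's contrast.
- A reader might infer that the trial is underpowered for this reason. That requires an effect near 1.1 ml/kg/min or below, a substantial share using the same product, and a large loss of benefit in those users.
- A reader might infer that the washout fails. A user is never free of the agent, but steady own intake is not carryover of the study dose.

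**Conclusion.** The gap is real. Following sections 4.6 and 3.2 as written, a current user of CoQ10 or NR may remain on it through placebo and washout. This is a permission the plan grants, not merely a missing detail.

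The consequence is conditional. That user's placebo period is not free of the agent, and the biomarker reference values may be raised. The contrast for that agent is diluted if the response is non-additive. The size cannot be stated, because neither the prevalence of use nor the response of users is in the documents. The worst-case figures above are upper bounds on the dilution from stable use at each assumed share. They are of little consequence at 1 SD and appreciable near 0.53 SD.

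This is worth correcting because it is cheap to close. It is not a fatal flaw, and nothing in the documents shows that contamination occurs.

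**What to change.** 1. Add current personal use of non-study CoQ10 or NR to the exclusion criteria in section 3.2. The existing exception in section 4.6 then covers both products.
2. Record such use at visits 2, 3 and 4 as well as at baseline, and add this to Table 1.
3. Prespecify a sensitivity analysis of the primary endpoint that flags affected periods, using those records and the planned drug level/NAD samples. Define the flag before unblinding. The samples are informative about own use of an agent mainly at baseline, in the placebo period and in the other agent's period, since study supply raises the level in its own period.

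The cost is that a few screened patients become ineligible and one question is added per visit. No new samples are needed. How to manage an individual participant found to be using these products is for the sponsor to decide.
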